12.10.7.8 End of Participation

Participants will remain under the care of their local clinicians and/or primary neurologists while in this study. Participants will be informed of any clinically relevant findings identified during the study via secure e-mail. Participants will also be provided with a letter to give to their primary care provider detailing such findings. Participation in this study will be considered to have ended once the participant has completed the Day 42 post-intervention TEAE assessment (exceptions to this may be made on a case-by-case basis e.g. if an individual has an ongoing AE/SAE at Day 42).

12.10.8 Pharmacokinetic Assessments

12.10.9 Blood Sampling and Processing

For all subjects, blood samples for the determination of S 48168 (ARM210) will be collected into polypropylene heparinized tubes at scheduled time points as delineated in the Study Events Flow Chart ([Section 7](#)). All attempts will be made to collect the blood samples at, or within \pm 15 minutes of the scheduled time point. Actual sample times will be recorded.

Within 30 minutes from collection, PK blood samples will be centrifuged at approximately 2000 g for 10 minutes, at approximately 4°C.

After centrifugation, plasma will be transferred into aliquots (polypropylene tubes) containing approximately 0.3 mL/tube. The plasma aliquots will be frozen at $-80 \pm 10^\circ\text{C}$ within 30 minutes maximum from the end of centrifugation. Samples will be stored at this temperature until shipped to the bioanalytical laboratory.

12.10.10 Interim PK Analysis

Interim PK analysis was conducted by the contract vendor (Nuvisan) as follows:

Full PK once the first dose group (120 mg/day) have completed dosing for approximately 28 days (not to exceed 30 days) ([Section 13.1](#)).

Interim analysis of Cmax once the first 3 participants in the second dose group (≤ 200 mg/day) have completed dosing for approximately 28 days (not to exceed 30 days).

Provided that the Cmax limit of 35 ug/mL is not exceeded in the above samples, all remaining PK analyses will be conducted upon study completion.

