Using total PK to determine the safety margin, the Cmax should be limited to 35 ug/ml per the FDA partial clinical hold comments. This limit is based on a 10-fold safety margin to the Cmax of the high dose of the 13-week dog toxicology study. We propose to dose the first three participants at 120 mg/day. The mean Cmax for healthy volunteers at this dose was 17 ug/ml. Assuming the safety, tolerability and PK are acceptable [REDACTED]

[REDACTED] to the DSMB, a top dose of \leq [REDACTED] (not to exceed 30 days) is proposed for the remaining participants.

Preliminary human PK of 14 days of dosing at 240 mg/day S48168 (ARM210) shows a mean Cmax of 35 ug/ml [REDACTED]. The Cmax at steady state has been dose proportional, with no evidence of non-linearity, with low variability (13.5%). The projected Cmax for 200 mg/day at steady state is 28 ug/ml. Assuming that the PK at 120 mg/day dose is similar to the previous numbers seen in healthy volunteers, then a dose \leq 200 mg/day should remain below the dose cap of 35 ug/ml.

Staggered dosing was implemented for the first three participants at the low dose level, starting each participant on drug after the previous participant had finished 14 days of dosing. At the high dose level (200 mg/day), Cmax at steady state of each participant was measured before dosing the next participant. S48168 (ARM210) reaches steady state typically after five days of dosing, consistent with its terminal half life. PK profiles have been established in RYRI-RM trial participants at both low and high dose levels and are consistent with healthy volunteer studies. In addition, none of the subjects tested so far have exceeded the FDA Cmax limit of 35 ug/ml at steady state and no clear safety signals have been observed to date in safety labs, EKG, or other safety related assessments.

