The PK profile of the 240 mg dose at steady state in healthy volunteers shows a slow decline over several days at the end of drug administration (Figure 2). This gradual decline in exposure reduces the risk of a sudden effect at the end of the dosing period due to withdrawal.

[figure not shown]

Figure 2. PK profile of S 48168 (ARM210) at day 1 and day 14 in healthy volunteers dosed at 240mg/day.

Modification of the Dose and/or Dosing Regimen

This protocol is written with some flexibility to accommodate the inherent dynamic nature of early clinical trials. Modifications to the dose and dosing regimen currently outlined below may be required to achieve the scientific goals of the trial objectives and/or to ensure appropriate safety monitoring of the trial subjects.

As such, lowering the currently outlined dose may be permitted based on newly available data, but the dose may not exceed 200 mg per day.

- Decrease in the dose of the trial drug administered during the study

The current top dose of \leq 200 mg/day (10 X 20 mg tablets) is not expected to exceed the Cmax limit of 35 ug/ml (projected mean from healthy volunteer data of 28 ug/ml). However if PK monitoring reveals that the limit could be exceeded, then 180 mg/day will be given (9 X 20 mg tablets). This dose would be projected to have a Cmax of 25.75 ug/ml.

- Decrease in the duration of trial drug administration (e.g., number of days) in the study
- Addition of a pharmacokinetic data review

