11.8.4 Interim Analysis (PK)

Interim PK analysis was conducted by Nuvisan (contract vendor) as follows:

First dose group (120 mg/day): Full PK analysis once the first three participants completed dosing for approximately 28 days (not to exceed 30 days). This allowed verification that the observed PK results from these *RYR1*-RM affected individuals agreed with PK results from previous studies in healthy volunteers and that the Cmax limit of 35 ug/mL was not exceeded. At this stage of drug development, a PK value that would not require a dose adjustment would be considered as similar. This would mean 50% lower or 200% higher than that of healthy volunteers.

Based on PK results and safety data from the first dose group, the dose to be administered in subsequent participants was increased to 200 mg/day. This was based on DSMB recommendations and investigator and sponsor's joint decision.

Second dose group (200 mg/day): PK analysis for Cmax once the first three participants have completed dosing for approximately 28 days (not to exceed 30 days). This will allow verification that the Cmax limit of 35 ug/mL was not exceeded. Subsequently, all remaining samples will be shipped to the contract laboratory for analysis at the end of the study, when full PK analysis beyond the Cmax measurement will occur for all of the samples obtained from this group

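### After the passed three-participant Cmax check at 200 mg/day, no new Cmax result is scheduled until study completion, so the 180 mg/day rule gets no fresh data while later participants are dosed

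*Protocol*

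**What the plan says.** Protocol 9.5 caps Cmax at 35 µg/mL, following FDA partial clinical hold comments. It projects a mean of 28 µg/mL at 200 mg/day and keeps a fallback: "However if PK monitoring reveals that the limit could be exceeded, then 180 mg/day will be given". The projected Cmax at 180 mg is 25.75 µg/mL. The same section lists, as a permitted modification, "Addition of a pharmacokinetic data review", without saying when or on what evidence.

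Protocol 11.8.4 and 12.10.10 set the assay schedule: full PK after the 120 mg group, then Cmax after the first three participants at 200 mg. After that, 11.8.4 says "all remaining samples will be shipped to the contract laboratory for analysis at the end of the study", and 12.10.10 says "all remaining PK analyses will be conducted upon study completion", provided the limit was not exceeded. SAP 4.2 gives the same sequence.

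On results so far, Protocol 9.5 states that "none of the subjects tested so far have exceeded the FDA Cmax limit of 35 ug/ml at steady state". It adds that at 200 mg "Cmax at steady state of each participant was measured before dosing the next participant", and that patient PK at both doses is consistent with healthy volunteers.

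Three participants have been dosed at each level (11.1). The target is about 8-20 completers, and the 120 mg participants may re-enrol at 200 mg (Synopsis). Cmax above 35 µg/mL is an adverse event of special interest (12.10.7.7), and these events are part of the primary endpoint (10.2).

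**The concern.** The 180 mg rule depends on what PK monitoring reveals, but the scheduled monitoring ended with the third participant at 200 mg. Nothing else on the schedule replaces it:

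- The Day 13 trough is limited to the first six subjects (13.1).
- The steady-state profile is drawn around the final dose (Study Events Flow Chart, footnote i).
- New starts are limited to two per week, with no Cmax result required (11.8.1).
- Decisions to stop dosing or the study use PK data only if available (11.8.5).
- The sentence on measuring each high-dose Cmax before the next participant is in the past tense and describes people already dosed.

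What could be lost is the chance to update the estimate of the patient mean and spread, and to use the 180 mg option, while participants are still to be dosed. The DSMB meets monthly (12.10.7.3) but would see later exceedances only after nobody's dose can change.

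**Working it through.** **Inputs (Protocol 9.5 unless stated).** Mean steady-state Cmax in healthy volunteers: 17 µg/mL at 120 mg and 35 at 240 mg. Projected means: 28 at 200 mg and 25.75 at 180 mg. CV: 13.5% in 9.5, about 15% in 12.10.3. Cap: 35. Participants dosed so far: 6 (11.1).

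**Reproducing the projection.** Dose-proportional scaling gives 17 × 200/120 = 28.3, which agrees with the stated 28. Scaling from 240 mg gives 35 × 200/240 = 29.2, about 4% higher. For 180 mg the two scalings give 25.5 and 26.25; the stated 25.75 lies between them.

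**Chance that one participant exceeds 35.** I assume that healthy-volunteer values carry over to patients.

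- Normal: p = 1 − Φ((35 − m)/(m × CV)). For m = 28 and CV 13.5%, z = 7/3.78 = 1.85 and p = 3.2%.
- Log-normal: s² = ln(1 + CV²) and p = 1 − Φ((ln 35 − ln m + s²/2)/s). For the same inputs, s = 0.134, z = 1.73 and p = 4.2%.

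**Chance of at least one exceedance.** 1 − (1 − p)ⁿ, with independent draws. The remaining number n runs from 8 − 6 = 2 to 20 − 6 = 14.

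| Mean, CV | One participant | n = 2 | n = 14 |
|---|---|---|---|
| 28, 13.5% | 3.2-4.2% | 6-8% | 37-45% |
| 28, 15% | 4.8-5.8% | 9-11% | 50-57% |
| 29.2, 15% | 9.1-9.8% | 17-19% | 74-76% |
| 25.75 (180 mg), 13.5-15% | 0.4-1.7% | 1-3% | 5-21% |

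Each range runs from normal to log-normal; the last row also spans the two CVs. If three of the 14 are re-enrolled and not counted as fresh draws, n = 11. At mean 28 and CV 13.5% the chance is then 30-38%. If the three re-enrolments come on top of 20, n = 17 and the range at mean 28, CV 13.5-15%, is 43-64%.

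**What the first six patients already show.** Pooling both doses by proportionality, the standard error of the mean is 13.5%/√6 = 5.5%, or about 1.5 µg/mL at 28. A true patient mean of 32 would lie (32 − 28)/1.54 = 2.6 standard errors away. A mean of 30 would lie 1.3 away, so it is not excluded; at 30, about 11% of individuals would exceed 35 (CV 13.5%).

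**Re-enrolled participants.** A 120 mg Cmax that predicts 35 at 200 mg is 35 × 120/200 = 21.0 µg/mL. The matching threshold for 180 mg is 35 × 120/180 = 23.3.

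**Reach of rolling assays.** The first new result returns at 28 + T days. T is not in the documents; I assume 14-42 days. Participants started by then = 1 + floor(starts per month × (28 + T)/30.4). The recruitment rates come from Protocol 12.1.

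| Rate | Started by first result | Starting later, of 14 | Starting later, of 2 |
|---|---|---|---|
| 8 in 12 months | 1-2 | 12-13 | 0-1 |
| 8 in 6 months | 2-4 | 10-12 | 0 |
| 20 in 12 months | 3-4 | 10-11 | 0 |
| 20 in 6 months | 5-8 | 6-9 | 0 |
| Two per week (11.8.1 ceiling) | 12 or more | 0-2 | 0 |

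With two remaining, only the slowest rate with 14 days' turnaround reaches anyone.

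**The case against.** The best defence is that this was a deliberate sequential check, completed and passed. It was itself a planned input to the dose of the remaining participants, so a reader who infers that the 180 mg rule never had one would be wrong. Nor is further input ruled out. Section 9.5 permits a PK review, and the blood-volume tables in 12.11 allow extra blood for PK. The DSMB charter and medical monitoring plan, which are not in the file, may say more. All of this stands; what remains is that no further result is scheduled and the optional review has no trigger.

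A reader might also treat the check as three pass/fail results and call it nearly uninformative. That is too strong. The sponsor holds continuous Cmax values from six patients, described as consistent with healthy volunteers, and a mean as high as 32 is hard to reconcile with that. Poor CYP2C8 metabolizers and users of significant CYP2C8 inhibitors are excluded as well (11.6).

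Finally, samples are drawn at the last dose, so an assay cannot help the person sampled, and at a total of 8 or with fast enrolment it helps few or none. This limits the benefit of rolling assays. It does not touch the re-enrolment check, which uses values already in hand. Nothing in the documents shows that those individual values were ignored; the protocol simply does not require the check.

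**Conclusion.** The point holds as a scheduling gap: after a passed check there is no new scheduled Cmax result until study completion, although a live dose-reduction rule depends on such results. On healthy-volunteer inputs (mean 28, CV 13.5-15%), 3-6% of individuals would exceed 35 µg/mL. The chance of at least one exceedance is 6-11% in 2 more participants and 37-57% in 14. These figures assume that healthy-volunteer values carry over to patients, that draws are independent, and that the distribution is normal or log-normal. The sponsor's patient values should replace them.

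Two stronger inferences are not supported. The first is that later participants face demonstrated harm. The cap is conservative: 14 days at 240 mg/day in healthy volunteers "shows a mean Cmax of 35 ug/ml" and was well tolerated, though those were healthy men and not patients dosed for 28 days. The second is that late Cmax results would drop out of the primary endpoint. SAP 6.3 tabulates all events of special interest. It does not say how a PK result becomes one, but the safety shells are explicitly deferred, so this is unfinished detail. The same applies to 11.8.5, which does not make clear whether Cmax above 35 alone halts dosing.

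The change is worth making as an inexpensive improvement.

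**What to change.** 1. **Re-enrolled participants, at any sample size.** Before re-dosing at 200 mg, multiply the person's own 120 mg steady-state Cmax by 200/120. If the 120 mg value is above about 21 µg/mL, refer to the sponsor and DSMB for a start at 180 mg or lower. Above about 23.3, 180 mg is also predicted to breach the cap. This uses existing data.
2. **If enrolment goes beyond 8.** Amend Protocol 11.8.4 and 12.10.10, and SAP 4.2 to match, so that Day 28 samples already collected are assayed for Cmax in rolling batches and reported at the monthly DSMB meetings, with no enrolment hold. The purpose is to update the group mean and spread. One isolated exceedance is expected at these rates and need not change the dose; that decision stays with the sponsor and DSMB.

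**Cost.** Several small shipments and assay runs instead of one, and a short wording amendment. No extra patients, blood draws or enrolment delay. The benefit of step 2 goes only to participants who start after results return, which is few or none with fast enrolment or a total of 8.

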12.10.11 Analytical Method

Samples will be assayed for plasma S 48168 (ARM210) using a validated HPLC-MS-MS bioanalytical method. The subjects to include in the analysis are specified in [Section 13.2.2](#).

This analysis will be conducted by the contract vendor, Nuvisan. Since this is the first study of S 48168 (ARM210) in the *RYR1-RM* population, and profiling of S 48168 (ARM210) metabolism is currently ongoing in healthy volunteers, the remaining portions of plasma samples collected for PK analysis may be preserved for S 48168 (ARM210) metabolite analysis.

12.11 Blood Volume Drawn for Study Assessments

Table 1: Approximate Blood Volume During the Study (drug naïve participants)

Sample Type	Number of Time Points	Approximate Volume per Time Point * (mL)	Approximate Sample Volume Over Course of Study (mL)
Screening laboratory safety tests (including hematology, serum chemistry, serology) FSH (for postmenopausal female subjects only), and serum pregnancy (for female subjects only)	1	12.5	12.5
Screening CYP2C8 genotyping	1	4	4
On-study (including follow-up) hematology, serum chemistry, and serum pregnancy (as scheduled for female subjects only)	3	12.5	37.5
Blood for S 48168 (ARM210)	16	2	32
Baseline blood (future research use)	1	50.0	50.0
Post-intervention blood (future research use)	1	10.0	10.0
Total Blood Volume (mL)→			146.0**

* Represents the largest collection tube that may be used for this (a smaller tube may be used).

** If additional safety or PK analysis is necessary or if larger collection tubes are required to obtain sufficient plasma/serum for analysis, additional blood may be obtained (up to a maximum of 50 mL).

Table 2: Approximate Blood Volume During the Study (re-enrolled participants)

Sample Type	Number of Time Points	Approximate Volume per Time Point * (mL)	Approximate Sample Volume Over Course of Study (mL)
Screening laboratory safety tests (including hematology, serum chemistry, serology) FSH (for postmenopausal female subjects only), and serum pregnancy (for female subjects only)	1	12.5	12.5
Screening CYP2C8 genotyping	0	0	0
On-study (including follow-up) hematology, serum chemistry, and serum pregnancy (as scheduled for female subjects only)	3	12.5	37.5
Blood for S 48168 (ARM210)	8	2	16
Blood for future research use	2	10.0	20.0
Total Blood Volume (mL)→			86.0**

* Represents the largest collection tube that may be used for this (a smaller tube may be used).

** If additional safety or PK analysis is necessary or if larger collection tubes are required to obtain sufficient plasma/serum for analysis, additional blood may be obtained (up to a maximum of 50 mL).

13 DATA ANALYSIS

Data will be handled and processed according to Celerion Standard Operating Procedures, which are written based on the principles of GCP.

13.1 Pharmacokinetic Parameters

The following PK parameters for plasma S 48168 (ARM210) will be calculated, as appropriate:

Day 1

AUC0-24: The area under the concentration-time curve, from time 0 to the 24 hours post dose, as calculated by the linear trapezoidal method.

AUC0-t: The area under the concentration-time curve, from time 0 to the last observed non-zero concentration, as calculated by the linear trapezoidal method.

AUC0-inf: The area under the concentration-time curve from time 0 extrapolated to infinity. AUC0-inf is calculated as the sum of AUC0-t plus the ratio of the last measurable plasma concentration to the elimination rate constant.

AUC%extrap: Percent of AUC0-inf extrapolated, represented as $(1 - AUC0-t/AUC0-inf) * 100$.

Cmax: Maximum observed concentration.

Tmax: Time to reach Cmax. If the maximum value occurs at more than one time point, Tmax is defined as the first time point with this value.

Kel: Apparent first-order terminal elimination rate constant calculated from a semi-log plot of the plasma concentration versus time curve. The parameter will be calculated by linear least-squares regression analysis using the maximum number of points in the terminal log-linear phase (e.g., three or more non-zero plasma concentrations).

t½: Apparent first-order terminal elimination half-life will be calculated as $0.693/Kel$.

Tlag: Lag time – the time delay between drug administration and the onset of absorption; where onset of absorption can be defined as: the time point prior to the first observed/measured non-zero plasma concentration.

Day 28 (not to exceed Day 30)

AUC _{tau}	The area under the concentration-time curve during a dosing interval (tau) at steady state.
C _{max} :	Maximum observed concentration.
T _{max} :	Time to reach C _{max} . If the maximum value occurs at more than one time point, T _{max} is defined as the first time point with this value.
C _{min}	Minimum observed concentration.
T _{min}	Time to reach C _{min} .
RAAUC	The ratio of accumulation for AUC calculated as the ratio of the AUC _{tau} Day 28 (not to exceed Day 30)/AUC ₀₋₂₄ Day 1.
RAC _{max}	The ratio of accumulation for C _{max} calculated as the ratio of the C _{max} Day 28 (not to exceed Day 30)/C _{max} Day 1.

Concentration observed at the end of the dosing interval on Day 13 Ctrough (associated with Day 14 pre-dose) will be ascertained for the first six subjects. Additional parameters may be calculated as appropriate.

No value for Kel, AUC_{0-inf}, AUC%extrap, or t_{1/2} will be reported for cases that do not exhibit a terminal log-linear phase in the concentration-time profile.

No PK parameters will be calculated for subjects with 2 or fewer consecutive time points with detectable concentrations.

Individual and mean plasma concentration time curves (both linear and log-linear) will be included in the final report.

13.2 Statistical Methods

Detailed methodology for summary and statistical analyses of the data collected in this study will be documented in a Statistical Analysis Plan (SAP) (Appendix # 18). The SAP will be prepared by Celerion and agreed upon with the Sponsor. This document may modify the plans outlined in the protocol; however, any major modifications of the primary endpoint definition and/or its analysis will also be reflected in a protocol amendment. Additional statistical analyses other than those described in this section may be performed if deemed appropriate.

13.2.1 Determination of Sample Size

The sample size (n= 8) was determined based on the number of *RYR1*-RM affected individuals expected to have loss of RyR1-calstabin1 binding. This sample size is expected to be sufficient for analysis of the primary endpoint (safety and tolerability). The accrual ceiling for this study is n = 50 subjects to allow for dropout.

13.2.2 Subjects to Analyze

Safety Population: All subjects who received at least one dose of the study drug will be included in the safety evaluations.

PK Population: All subjects who comply sufficiently with the protocol (see Section 11.8.1) and display an evaluable PK profile (e.g., exposure to treatment, availability of measurements and absence of major protocol violations) will be included in the statistical analyses.

Pharmacodynamic/Target Engagement: All subjects who complete the study will be included in the pharmacodynamics/target engagement analysis.

Muscle/Motor Function (Grade Functional Tests and MFM32): All subjects who complete the study will be included in the muscle/motor function assessments.

Quality of Life: All subjects who complete the study will be included in the quality of life assessments.

13.2.3 Descriptive Statistics

Values will be calculated for the plasma concentrations and the PK parameters listed in [Section 13.1](#) using appropriate summary statistics to be fully outlined in the SAP.

PK data from [REDACTED] will be utilized for comparisons between healthy subjects and *RYR1*-RM patients.

13.3 Safety Evaluation

All safety data will be populated in the individual CRFs. All safety data will be listed by subjects.

Dosing dates and times will be listed by subject in their diary when not confined to the NIH CC.

AEs will be coded using the most current version of Medical Dictionary for Regulatory Activities (MedDRA®) available at Celerion and summarized by cohort and treatment for the number of subjects reporting the Treatment Emergent Adverse Events (TEAE) and the number of TEAEs reported. A by-subject AE data listing including verbatim term, coded term, treatment, severity, and relationship to treatment will be provided.

Safety data including ECGs, vital signs assessments, clinical laboratory evaluations, will be summarized by treatment and point of time of collection.

Descriptive statistics using appropriate summary statistics will be calculated for quantitative safety data as well as for the difference to baseline, when appropriate.

Concomitant medications will be listed by subject and coded using the most current version of WHO drug dictionary available at Celerion. Medical history will be listed by subject.

